APPENDIX 2A. SCHEDULE OF ASSESSMENTS FOR DAY 1 (Part 1)

Study Day	Day 1								
Timepoint	Predose			Drug Administration		EOI	1 hour postdose	6 hours postdose	12 hours postdose
Time (T) relative to infusion (h:min)	T = minus 01:00 – 00:00	T = minus 00:30 – 00:00	T = minus 00:15 – 00:00	T = 00:00	T = 00:30 – 01:00	T = 1:00 – 1:30	T = 02:00 (± 15 min)	T = 07:00 (± 15 min)	T = 13:00 (± 15 min)
BGB-DXP604 single dose administration				Start infusion	Stop infusion				
Vital signs	X						X	X	X
Targeted physical examination		X							
12-lead ECG	X						X	X	X
Cardiac telemetry ^a	X								
Prior/Concomitant medications review ^a	X								
Adverse event review ^a	X								
PK blood sampling	X					X		X (± 2 h)	
ADA sampling	X								

Abbreviations: ADA, antidrug antibody; ECG, electrocardiogram; EOI, end of infusion; h, hour; min, minutes; PK, pharmacokinetics.

^a Cardiac telemetry, prior/concomitant medications review, and adverse event review will be performed throughout the Day 1.

NOTE: The timepoints of predose are the time relative to the start of infusion whereas the timepoints of postdose are the time relative to the end of infusion.

APPENDIX 2B. SCHEDULE OF ASSESSMENTS FOR DAY 1 (Part 2)

Study Day	Day 1											
Timepoint	Predose			Drug Administration					EOI	1 hour postdose	6 hours postdose	12 hours postdose
Time (T) relative to infusion (h:min)	T = minus 01:00 – 00:00	T = minus 00:30 – 00:00	T = minus 00:15 – 00:00	T = 00:00	T = 00:30 – 01:00	T = 1:00 – 1:30	T = 1:30	T = 2:00 – 2:30	T = 2:30 – 3:00	T = 03:30 (± 15 min)	T = 08:30 (± 15 min)	T = 14:30 (± 15 min)
BGB-DXP593 single dose administration				Start infusion	Stop infusion							
BGB-DXP604 single dose administration						Prepare infusion	Start infusion	Stop infusion				
Vital signs	X									X	X	X
Targeted physical examination		X										
12-lead ECG	X									X	X	X
Cardiac telemetry ^a	X											
Prior/Concomitant medications review ^a	X											
Adverse event review ^a	X											
PK blood sampling (DXP604 and DXP593)	X								X		X (± 2 h)	
ADA sampling (DXP604 and DXP593)	X											

Abbreviations: ADA, antibody antidrug; ECG, electrocardiogram; EOI, end of infusion; h, hour; min, minutes; PK, pharmacokinetics.

^a Cardiac telemetry, prior/concomitant medications review, and adverse event review will be performed throughout the Day 1.

NOTE: The timepoints of predose are the time relative to the start of infusion whereas the timepoints of postdose are the time relative to the end of infusion.

APPENDIX 3. PHARMACOKINETIC AND ANTIDRUG ANTIBODY BLOOD SAMPLING)

APPENDIX 3A. PHARMACOKINETIC AND ANTIDRUG ANTIBODY BLOOD SAMPLING (Part 1)

Study Day	D1			D2	D3	D4	D5	D8	D15	D22	D29	D43	D57	D71	D85	D113 /EOS
Hours post infusion	0 (predose)	EOI	6	24	48	72	96	168	336	504	672	1008	1344	1680	2016	2688
Window Period (hours)	-60 min to predose	Within 30 min after EOI	± 2	± 6	± 6	± 6	± 6	± 6	± 24	± 24	± 24	± 48	± 48	± 48	± 48	± 48
PK blood sampling	X	X	X	X	X	X	X	X	X	X	X	X	X	X	X	X
ADA sampling	X								X		X		X		X	X

Abbreviations: ADA, antidrug antibody; D, day; EOI, end of infusion; EOS, End-of-Study; min, minutes; PK, pharmacokinetic.

Note: Sample collection must be from the opposite arm that is used for study drug infusion. Refer to laboratory manual for detailed collection instructions.

APPENDIX 3B. PHARMACOKINETIC AND ANTIDRUG ANTIBODY BLOOD SAMPLING (Part 2)

Study Day	D1			D2	D3	D4	D5	D8	D15	D22	D29	D43	D57	D71	D85	D113 /EOS
Hours post infusion	0 (predose)	EOI ^b	6 ^b	24	48	72	96	168	336	504	672	1008	1344	1680	2016	2688
Window Period (hours)	-60 min to predose ^a	Within 30 min after EOI of second infusion	± 2	± 6	± 6	± 6	± 6	± 6	± 24	± 24	± 24	± 48	± 48	± 48	± 48	± 48
PK blood sampling	X	X	X	X	X	X	X	X	X	X	X	X	X	X	X	X
ADA sampling	X								X		X		X		X	X

Abbreviations: ADA, antidrug antibody; D, day; EOI, end of infusion; EOS, End-of-Study; min, minutes; PK, pharmacokinetics.

^a Predose PK and ADA samples for both BGB-DXP604 and BGB-DXP593 may be collected together before the first infusion.

^b EOI and 6 hours PK samples for both BGB-DXP604 and BGB-DXP593 may be collected together.

Note: Sample collection must be from the opposite arm that is used for study drug infusion. Refer to laboratory manual for detailed collection instructions.

APPENDIX 4. CLINICAL LABORATORY ASSESSMENTS

Clinical chemistry	Hematology	Coagulation	Urinalysis ^a
Alkaline phosphatase Alanine aminotransferase Aspartate aminotransferase Albumin Total bilirubin Direct bilirubin Blood urea nitrogen or urea Potassium Sodium Total calcium Creatinine Glucose Lactate dehydrogenase Total protein Magnesium Lipase Amylase	Red blood cell count Hematocrit Hemoglobin Platelet count White blood cell count with differential (both absolute count and percentage) 
 • Lymphocyte count • Neutrophils • Monocytes • Eosinophils • Basophils 	Prothrombin time Partial thromboplastin time or activated partial thromboplastin time International normalized ratio	Specific gravity pH Glucose Protein Blood Ketones Bilirubin Urobilinogen Nitrite Leukocyte
Other Screening Tests			

 • Follicle-stimulating hormone and estradiol (as needed for female subjects who are < 55 years of age with no spontaneous menses for ≥ 12 months to identify the status of no childbearing potential) • Urine (drugs screen [to include at minimum: amphetamines, barbiturates, benzodiazepines, cocaine, opiates, methamphetamines, methadone, methyl enedioxy methamphetamine, phencyclidine, and tetrahydrocannabinol]) • Breath test (alcohol screen) • Highly sensitive (serum/urine) human chorionic gonadotropin pregnancy test (as needed in female subjects of childbearing potential) • Serology: 
 - HIV antibody - hepatitis B surface antigen, hepatitis B core antibody, hepatitis C virus antibody - IgG antibodies against SARS-CoV-2 • Virology: nasopharyngeal or oropharyngeal swab for COVID-19 rRT-PCR test 
The results of each test must be entered into the CRF.
			

Abbreviations: COVID-19, Coronavirus Disease 2019; CRF, case report form; HIV, human immunodeficiency virus; Ig, immunoglobulin; pH, negative of the logarithm to base 10 of the activity of the (solvated) hydronium ion; rRT-PCR, real-time reverse transcription polymerase chain reaction; SARS-CoV-2, severe acute respiratory syndrome coronavirus 2.

^a The urine microscopy will be performed if the urinalysis parameter, such as leukocyte, is out of normal range.

APPENDIX 5. CONTRACEPTION GUIDELINES AND DEFINITIONS OF “WOMEN OF CHILDBEARING POTENTIAL”, “NO CHILDBEARING POTENTIAL”

Contraception Guidelines

The Clinical Trials Facilitation Group’s recommendations related to contraception and pregnancy testing in clinical trials include the use of highly effective forms of birth control ([Clinical Trials Facilitation Group 2014](#)). These methods include the following:

- Combined (estrogen- and progestogen-containing) hormonal contraception associated with the inhibition of ovulation
 - Oral, intravaginal, or transdermal
- Progestogen-only hormonal contraception associated with the inhibition of ovulation:
 - Oral, injectable, or implantable
Note: Oral birth control pills are not considered a highly effective form of birth control, and if they are selected, they must be used with a second, barrier method of contraception such as condoms with or without spermicide.
- Intrauterine device
- Intrauterine hormone-releasing system
- Bilateral tubal occlusion
- Vasectomized male partner
Note: This is only considered a highly effective form of birth control when the vasectomized partner is the sole partner of the study participant and there has been a medical assessment confirming surgical success.
 - A sterile male is one for azoospermia has been demonstrated in a semen sample examination as definitive evidence of infertility.
- Sexual abstinence (defined as refraining from heterosexual intercourse during the entire period of exposure associated with the study treatment).
NOTE: Total sexual abstinence should only be used as a contraceptive method if it is in line with the subject’s usual and preferred lifestyle. Periodic abstinence (eg, calendar, ovulation, symptothermal, or postovulation methods), declaration of abstinence for the duration of exposure to study drug(s), and withdrawal are not acceptable methods of contraception.

Of note, barrier contraception (including male and female condoms with or without spermicide) is not considered a highly effective method of contraception and if used, this method must be combined with another acceptable method listed above.

Definitions of “Women of Childbearing Potential,” “Women of No Childbearing Potential”

As defined in this protocol, “women of childbearing potential” are female subjects who are physiologically capable of becoming pregnant.

Conversely, “women of no childbearing potential” are defined as female subjects meeting any of the following criteria:

- Surgically sterile (ie, through bilateral salpingectomy, bilateral oophorectomy, or hysterectomy)
- Postmenopausal, defined as:
 - ≥ 55 years of age with no spontaneous menses for ≥ 12 months OR
 - < 55 years of age with no spontaneous menses for ≥ 12 months AND with a postmenopausal follicle-stimulating hormone (FSH) concentration > 30 IU/mL and all alternative medical causes for the lack of spontaneous menses for ≥ 12 months have been ruled out, such as polycystic ovarian syndrome, hyperprolactinemia, etc.

If an FSH measurement is required to confirm postmenopausal state, concomitant use of hormonal contraception or hormonal replacement therapy should be excluded.

Adapted from [Clinical Trials Facilitation Group 2014](#).

Signature Page for VV-CLIN-035599 v1.0

Approval	 Clinical Development 23-Nov-2020 03:04:22 GMT+0000
----------	--

Signature Page for VV-CLIN-035599 v1.0

**LIST OF ABBREVIATIONS AND DEFINITIONS OF TERMS**

Abbreviation	Definition
ADA	antidrug antibody
AE	adverse event
ATC	anatomical therapeutic chemical
AUC	area under the concentration-time curve
BGB-DXP593	code name for monoclonal antibody BGB-DXP593, also named DXP593, BD-368-2, and WBP2281
BGB-DXP604	code name for monoclonal antibody BGB-DXP604, also named DXP-604, BD-604, and WBP2316
BLQ	below the assay quantification limit
BMI	body mass index
CL	clearance
C max	maximum observed concentration
CV	coefficient of variance
ECG	electrocardiogram
eCRF	electronic case report form
LLOQ	lower limit of quantitation
MedDRA ®	Medical Dictionary for Regulatory Activities
NAb	Neutralizing antibody
NCI-CTCAE	National Cancer Institute Common Terminology Criteria for Adverse Events
PK	pharmacokinetic
PT	preferred term
SAE	serious adverse event
SAP	statistical analysis plan
SMC	Safety Monitoring Committee
SOC	system organ class
SD	standard deviation
TEAE	treatment-emergent adverse event
t 1/2	terminal half-life
t max	time to maximum observed concentration
V Z	volume of distribution
WHO DD	world health organization drug dictionary

## 1. INTRODUCTION

The purpose of this statistical analysis plan (SAP) is to describe the procedures and the statistical methods that will be used to analyze and report results for BGB-DXP604-101, A Phase 1, Randomized, Double-Blind, Placebo-Controlled Study to Evaluate the Safety, Tolerability, Pharmacokinetics, and Immunogenicity of BGB-DXP604 Alone and in Combination With BGB-DXP593 in Healthy Subjects. The focus of this SAP is for the planned final analysis specified in the study protocol.

Reference materials for this statistical plan include the BGB-DXP604-101 Original Protocol dated on 23 November 2020.

## 2. STUDY OVERVIEW

This is a phase 1, randomized, double-blind, placebo-controlled study to investigate the safety, tolerability, pharmacokinetics, and immunogenicity of BGB-DXP604 alone and in combination with BGB-DXP593 in healthy subjects.

After providing written informed consent, subjects will complete all screening assessments. After being confirmed as eligible, subjects will be sequentially enrolled for 2 cohorts of different dose levels (referred to as Part 1). Two dose levels are planned for eligible subjects to receive a single intravenous dose of study drug (ie, BGB-DXP604 or placebo) at 10 mg/kg or 30 mg/kg, respectively.

Enrollment will begin at the 10 mg/kg dose level. Each dose level of study drug evaluated may be referred to as a cohort or dose level.

In Part 2, the combination of BGB-DXP604 and BGB-DXP593 will be tested in eligible subjects. Subjects enrolled in Cohort 2A will either receive the combination of BGB-DXP604 and BGB-DXP593 or placebo (ie, the normal saline with volume equal to BGB-DXP604 or BGB-DXP593 via separate intravenous infusions). The doses of BGB-DXP604 and BGB-DXP593 will be recommended by SMC and not exceed 30 mg/kg for each study drug.

In this study, after the last subject in the current cohort has received the study drug and has been followed up for  $\geq 5$  days, the Safety Monitoring Committee (SMC) will review the available safety and laboratory data. The next cohort will be initiated after the SMC review. The dose level of BGB-DXP604 in Cohort 1B and Cohort 2A may be adjusted based on SMC recommendation.

In each cohort, eligible subjects will be randomized at a 3:1 ratio (6 active: 2 control) to the active arm for receiving the study drug(s) (ie, BGB-DXP604 alone or the combination of BGB-DXP604 and BGB-DXP593) or to the control arm for receiving placebo, respectively. For safety reasons, the sentinel dosing will be adopted for each cohort. In other words, 2 eligible subjects will be randomized at a 1:1 ratio (1 active: 1 control) to receive the study drug(s) or placebo on Day 1; the remaining subjects will be randomized at a 5:1 ratio (5 active: 1 control) to receive the study drug(s) or placebo  $\geq 48$  hours later, provided that satisfactory safety and tolerability has been demonstrated for the first 2 subjects randomized and dosed in the current cohort.

The planned cohorts and number of subjects in each cohort are provided in [Table 1](#). Up to 30 subjects (including possible replacement) will be enrolled in the study.

Subjects are expected to be available for follow-up visits until Day 113 of the study. Subjects will be replaced if they cannot complete the infusion or they do not receive any study drug after randomization. Subjects may be replaced if they discontinue from the study before Day 29.

**Table 1: Planned Cohorts and Number of Subjects in Each Cohort**

Part	Cohort	Number of Subjects	
		Active Arm	Control Arm (Normal Saline)
1: BGB-DXP604 alone	1A: 10 mg/kg	6	2
	1B: 30 mg/kg a	6	2
2: BGB-DXP604 + BGB-DXP593	2A: 30 mg/kg b BGB-DXP604 + 30 mg/kg b BGB-DXP593	6	2

Abbreviation: SMC, Safety Monitoring Committee.

a The dose level of BGB-DXP604 in Cohort 1B may be adjusted based on SMC recommendation.

b The doses of BGB-DXP604 and BGB-DXP593 in Cohort 2A will be recommended by SMC and not exceed 30 mg/kg for each study drug.

Subjects will be monitored for safety, tolerability, PK and immunogenicity of BGB-DXP604 and BGB-DXP593 throughout the study.

### 3. STUDY OBJECTIVES

#### 3.1. Primary Objective

- To investigate the safety and tolerability of BGB-DXP604 alone and in combination with BGB-DXP593 in healthy subjects

#### 3.2. Secondary Objective

- To characterize the PK profile of BGB-DXP604 when given alone in healthy subjects
- To characterize the PK profiles of BGB-DXP604 and BGB-DXP593 when given in combination in healthy subjects
- To evaluate the potential immunogenicity of BGB-DXP604 when given alone in healthy subjects
- To evaluate the potential immunogenicity of BGB-DXP604 and BGB-DXP593 when given in combination in healthy subjects

### 4. STUDY ENDPOINTS

#### 4.1. Primary Endpoint(s)

- Incidence and severity of treatment-emergent adverse events (TEAEs) and treatment-emergent serious adverse events (SAEs)

## 4.2. Secondary Endpoints

- Changes in vital signs and 12-lead electrocardiogram (ECG) parameters from baseline
- Incidence and magnitude of clinical laboratory abnormalities
- Characterize PK concentration-time profile and PK parameters for BGB-DXP604 and BGB-DXP593:  $C_{max}$ ,  $AUC_t$ ,  $AUC_{inf}$ ,  $AUC_{0-29}$ ,  $t_{max}$ ,  $t_{1/2}$ , CL, and  $V_z$  as appropriate
- Clinical immunogenicity of BGB-DXP604 and BGB-DXP593 evaluated through the detection of ADA over time

## 5. SAMPLE SIZE CONSIDERATIONS

A sample size of 8 subjects at each cohort (6 active and 2 control) totaling up to 30 subjects (including possible replacement) is not based on any statistical considerations. The sample size is based on the clinical consideration to provide safety and tolerability information and pharmacological considerations with the need to minimize exposure to healthy subjects in each cohort. No formal inferential statistics will be applied to the safety or PK data.

## 6. STATISTICAL METHODS

### 6.1. Analysis Sets

The Safety Analysis Set will include all the subjects who received either study drug. The Safety Analysis Set is used for all safety analyses.

The PK Analysis Set will include all the subjects who received either study drug and had any measurable concentration of study drug(s). The PK Analysis Set will be used for PK analyses.

The ADA Analysis Set include all the subjects who received either study drug and for whom both baseline ADA and at least 1 postbaseline ADA results are available. The ADA Analysis Set is used for immunogenicity analyses.

### 6.2. Data Analysis General Considerations

#### 6.2.1. Definitions and Computations

Study Day: study day will be calculated in reference to the date of the first dose of study drug. For assessments conducted on or after the date of the dose of study drug, study day will be calculated as (assessment date – the date of the dose of study drug + 1). For assessments conducted before the date of the dose of study drug, study day will be calculated as (assessment date – the date of the dose of study drug). There is no study day 0.

In the situation where the event date is partial or missing, the date will appear partial or missing in the listings. Study day and any corresponding durations will be presented based on the imputations specified in [Appendix A](#).

**Baseline:** baseline is defined as the last non-missing value collected before the first dose of study drug.

All subjects who received placebo from different cohorts will be pooled together into the placebo arm.

### 6.2.2. Conventions

Unless otherwise specified, the following conventions will be applied to all analyses:

- 1 year = 365.25 days. Number of years is calculated as (days/365.25) rounded up to 1 significant digit.
- 1 month = 30.4375 days. Number of months is calculated as (days/30.4375) rounded up to 1 significant digit.
- P-values will be rounded to 4 decimal places. P-values that round to 0.0000 will be presented as '< 0.0001' and p-values that round to 1.000 will be presented as '> 0.9999'.
- For laboratory results collected as  $\geq x$ , the value of the laboratory results will be set as x. For laboratory results collected as  $< x$ , the value of the laboratory results will be set as x divided by 2.
- For by-visit observed data analyses, percentages will be calculated based on the number of subjects with non-missing data as the denominator, unless otherwise specified.
- Unscheduled measurements and retested measurements will not be included in by-visit table summaries and graphs but will contribute to the best/worst case value where required (e.g. shift table). Listings will include scheduled, unscheduled and retest data.
- For continuous endpoints, summary statistics will include n, mean, standard deviation, median, Q1, Q3 and range (minimum and maximum).
- For discrete endpoints, summary statistics will include frequencies and percentages.

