10.3.3. Laboratory Analyses

Clinical laboratory (clinical chemistry, hematology, coagulation, and urinalysis) values will be evaluated for each laboratory parameter as appropriate. Abnormal laboratory values will be flagged and identified as those outside (above or below) the normal range. Laboratory parameters and their changes from baseline will be summarized by visit and treatment group. Changes from baseline will only be summarized for subjects with both baseline and postbaseline measurements.

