### 6.5.3. Laboratory Values

Clinical laboratory values will be evaluated for each laboratory parameter as appropriate.

Descriptive summary statistics (n, mean, standard deviation, median, Q1, Q3, minimum, and maximum for continuous variables; n [%] for categorical variables) for laboratory parameters and their changes from baseline will be summarized by visit and treatment group. Change from baseline will only be summarized for subjects with both baseline and postbaseline measurements. The percentage of abnormal values for laboratory parameters will be summarized by visit and treatment group.

Laboratory parameters that are graded in [NCI-CTCAE v5.0](#) will be summarized by shifts from baseline NCI-CTCAE grades to maximum postbaseline grades. In the summary of laboratory parameters by NCI-CTCAE grade, parameters with NCI-CTCAE grading in both high and low directions will be summarized separately.

Subject data listings of each parameter will be provided. Abnormal laboratory values will be flagged and identified as those outside (above or below) the normal range. Reference (normal) ranges for laboratory parameters will be provided.

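### The SAP's rule of halving laboratory results reported as < x has no exception for tests whose lower reporting limit is far from zero (specific gravity, pH, INR, clotting times), and could give impossible values in descriptive safety tables.

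*SAP*

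**What the plan says.** SAP 6.2.2 opens its list of conventions with "Unless otherwise specified, the following conventions will be applied to all analyses". One of them deals with laboratory results that arrive as inequalities. A result given as ≥ x takes the value x. For a result given as < x, "the value of the laboratory results will be set as x divided by 2".

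SAP 6.5.3 describes how the values are used: "laboratory parameters and their changes from baseline will be summarized by visit and treatment group", with "n, mean, standard deviation, median, Q1, Q3, minimum, and maximum for continuous variables" and counts with percentages for categorical ones. It does not say which parameters are continuous and which are categorical. Its only qualification is general: "Clinical laboratory values will be evaluated for each laboratory parameter as appropriate".

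Protocol 10.3.3 brings urine and clotting tests into the same analysis: "Clinical laboratory (clinical chemistry, hematology, coagulation, and urinalysis) values will be evaluated for each laboratory parameter as appropriate". In Protocol Appendix 4 the urinalysis column begins "Specific gravity pH Glucose Protein", and the coagulation column lists prothrombin time (PT), partial or activated partial thromboplastin time (PTT/aPTT) and INR.

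The only other below-limit rule is in SAP 6.6.2. It sets drug concentrations below the quantification limit to zero and does not concern safety laboratory tests.

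**The concern.** Replacing < x by x/2 is a reasonable convention when the result could lie anywhere between zero and x, as with a concentration whose reporting limit is close to zero. It fails when the limit is far from zero. Specific gravity is a ratio to water, so half of a limit near 1 describes urine about half as dense as water. Half of a pH reading has no meaning on a logarithmic scale. A clotting time or INR just under its lower reporting limit is not plausibly half of that limit.

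As written, the rule reaches all of these tests by default. With six subjects in an arm, one substituted value can move the arm's mean, SD, minimum and change from baseline a long way, although the true result may be only just below the limit. If the halved value is the baseline, that subject's change is pushed upward at every visit.

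**Working it through.** **Inputs from the documents.** The substitution is x/2 (SAP 6.2.2). The summaries include mean, SD, median, minimum and change from baseline (SAP 6.5.3). Each cohort has 6 active subjects (SAP 5). Placebo subjects are pooled over three cohorts (SAP 6.2.1), giving 3 × 2 = 6 as planned. The plan states no figure of its own to reproduce.

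**Assumptions, not in the documents.** Lower reporting limits are 1.005 for specific gravity, 5.0 for pH, 0.9 for INR and 9.0 s for PT. One subject of six has a < x result. The other five values are:

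- specific gravity 1.010, 1.012, 1.015, 1.018, 1.020
- pH 5.5, 6, 6, 6.5, 7
- INR 1.0, 1.0, 1.1, 1.0, 1.1
- PT 11, 11.5, 12, 12.5, 13 s

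**Shift in the mean.** Using x/2 instead of x lowers an arm mean by (x − x/2)/n = x/(2n), whatever the other values are. For specific gravity this is 1.005/(2 × 6) = 0.084.

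**Specific gravity in full.** The substituted value is 1.005/2 = 0.5025. The other five sum to 5.075.

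- Mean with x/2: (5.075 + 0.5025)/6 = 0.9296, which is below 1.000.
- Mean with x: (5.075 + 1.005)/6 = 1.0133.
- SD: 0.2093 with x/2 against 0.0055 with x, about 38-fold.
- Median: (1.012 + 1.015)/2 = 1.0135 either way.
- Minimum: 0.5025 against 1.005.
- Taking a baseline of 1.015 for all six, that subject's change is 0.5025 − 1.015 = −0.5125, against 1.005 − 1.015 = −0.010. The mean change is −0.0854 against −0.0017.
- If instead the baseline is the < 1.005 result and a later value is 1.015, the change is 1.015 − 0.5025 = +0.5125.

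**The tests side by side (one < x result in six):**

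| Test, assumed limit | Value under x/2 | Mean, x → x/2 | SD, x → x/2 |
|---|---|---|---|
| Specific gravity, 1.005 | 0.5025 | 1.013 → 0.930 | 0.0055 → 0.209 |
| pH, 5.0 | 2.5 | 6.00 → 5.58 | 0.71 → 1.59 |
| INR, 0.9 | 0.45 | 1.02 → 0.94 | 0.08 → 0.25 |
| PT, 9.0 s | 4.5 s | 11.50 → 10.75 s | 1.41 → 3.14 s |

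Specific gravity is the extreme case because its values span so narrow a range. For the other three the SD rises about two- to three-fold and the mean moves less.

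**How well x does instead.** If urine is no less dense than water, a true value below 1.005 lies between 1.000 and 1.005. Using x then misstates the arm mean by at most 0.005/6 = 0.0008. Using x/2 misstates it by at least (1.000 − 0.5025)/6 = 0.083.

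**The case against.** The strongest reply is that nothing in the documents says this will happen. They give no reporting limits and do not say that the local laboratory reports any of these tests as < x. If all results arrive as plain numbers, the rule never touches them. SAP 6.5.3 also allows categorical summaries without assigning parameters, so urinalysis may never enter a mean. This stands, and it makes the point conditional.

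A reader might infer that the rule will create a false drug or placebo effect. The documents do not support that. The laboratory outputs are descriptive, SAP 5 excludes formal inference on safety data, and the primary endpoint is adverse events. The same table would show an almost unchanged median beside an absurd minimum, which would point to an artefact.

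A reader might also infer that the secondary endpoint on the incidence of laboratory abnormalities is distorted. That would need a halved value to cross a reference limit or change a toxicity grade. The documents give no laboratory reference limits, and no changed flag or grade can be shown. A result already below range would be flagged low either way.

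Two defences are weaker. The general wording about evaluating each parameter as appropriate leaves room for judgement, but it is not a written exception. The outlier review in Protocol 15.1.3 concerns collected data, whereas the halved value is derived later.

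**Conclusion.** The rule is wrong as written for specific gravity, pH, INR, PT and PTT/aPTT. Where it applies to them, it yields an impossible or unphysiological value. Whether it will apply rests on two assumptions that the documents leave open: that the laboratory reports such results as < x, and that the parameters are summarised as continuous.

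If both hold, the damage is limited to the mean, SD, minimum and change from baseline in descriptive safety tables. It is large for specific gravity under the assumed limit and smaller for the other tests worked through; nothing was computed for PTT/aPTT. Low severity, but the correction is clear.

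**What to change.** In SAP 6.2.2, restrict the x/2 substitution to laboratory parameters whose lower reporting limit is near zero. State that for urine specific gravity, urine pH, INR, PT and PTT/aPTT a result collected as < x is set to x. This uses the boundary value, as the SAP already does for ≥ x.

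The cost is a sentence in the SAP and a short parameter list in the laboratory programming, with no change to data collection. It should be settled before database lock. Otherwise an odd value found later would have to be handled ad hoc by sponsor biostatistics staff, who are unblinded under Protocol 5.3.
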